The INSIGHT START study presents an opportunity to compare participant understanding after being randomized to either a standard consent form or a more concise consent form, across a variety of languages and international research sites. The main outcome measure will be prospective participant comprehension of the study specific information, and secondary outcome measures will include participant satisfaction with the consent process, and the resources required for this process. Demonstrating that one form is superior to the other would suggest a new standard or reinforce the current approach to writing consent forms. A demonstration of equivalent results would permit investigators to use the most efficient and easiest of equally effective alternatives.

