8.3.3 Study Hypothesis

Comprehension of those in the concise consent group will be at least as good as for those in the standard consent group. Satisfaction with the process will be higher for the concise group.

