Sample size for the START substudy is estimated using an approach described by Hayes and Bennett.¹⁰⁷ They use the between-site coefficient of variation (standard deviation divided by mean) to estimate sample size. Their approach is equivalent to use of the intra-site correlation coefficient. If a coefficient of variation of 0.30 is assumed and each site enrolls 25 participants, then 58 sites (29 assigned to use the concise consent and 29 assigned to use the standard consent) are required to detect a difference of 15% of participants responding accurately to the questions concerning randomization (50% versus 65%) with power of 0.80 at the two-sided level of significance of 0.05 (i.e., a total of 1,450 participants). If the coefficient of variation is 0.20, then a total of 34 sites are needed with these assumptions (850 participants). For comparison, if participants were individually randomized, a total of 340 participants would be required.

Sample size assumptions were assessed after approximately 500 participants were enrolled by 70 sites; the coefficient of variation was 0.17. Most of the participants enrolled had a primary language of English, Spanish or German. Since there is interest in obtaining data for other primary languages (e.g., Thai, Greek, Portuguese), for sites in developing countries, and for other subgroups, and since the substudy has proven to be very acceptable to participants and site staff, the Informed Consent substudy decided to offer new sites in START the opportunity to participate in the substudy. This will enhance the generalizability of the substudy.

Given the current site participation and enrollment per site, it is estimated that 125-150 sites will participate in the substudy with an average enrollment of 15 participants (an estimated 2,000 participants). This will provide greater than 90% power for the primary endpoint comparison related to comprehension of randomization and allow reliable comparisons between the standard and concise groups for other measures of comprehension that are being assessed as well as subgroups of interest.

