Purpose of the study: to evaluate understanding of study information and satisfaction with the consent process among participants of the START study after receiving information from one of two different consent forms: a standard or a concise consent form.

Hypothesis: comprehension for those receiving the concise consent form will be at least as good as for those who received the standard form. Satisfaction will be higher in the concise group.

Unit of randomization: site

Stratified randomization- grouped by primary language, and centrally assigned by block randomization within stratum

Primary endpoint- proportion of participants who answered the randomization questions correctly

Secondary endpoints-

Comprehension score (based on # of correct answers to knowledge questions)

Composite score of satisfaction

Composite score of voluntariness

There is limited info available on site to site variability in understanding randomization. Based on data from the ESPRIT study, estimated coefficient of variation for true proportions between sites was 0.30 and estimated intra-site correlation coefficient 0.09. Based on this, an estimated 58 sites are needed to show a difference of 15% between participants receiving each consent who respond accurately to questions about randomization with a power of 0.80 at the two sided level of significance of 0.05 (a total of 1450 participants). With 179 sites and 4150 participants in the substudy, our power is substantially increased, and we should be able to readily identify differences between consents in the level of understanding of randomization, even if the site-to-site variability is higher than that found in ESPRIT.

Logistic regression appropriate to cluster randomized trials will be used to compare groups for the primary outcome. Odds ratios and confidence intervals. Primary analysis will include all participants who completed the post-consent questionnaire.

Mean levels of continuous secondary outcomes accounting for within-site correlation, and using the intrasite correlation coefficient. Secondary analyses will include those who did not complete the questionnaire and count incomplete responses as incorrect responses.

Statistical analysis

Descriptive statistics by:

- two-way tables with counts and proportions for categorical variables. P-values by chi-square or exact tests

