- Median (IQR) (or mean-SD in a few cases) for continuous variables. P-values by Mann-Whitney/Kruskal-Wallis tests (or t-test/one way ANOVA respectively)
- Results shown by arm (i.e. consent assignment)

Univariable/multivariable analysis– *Correct answer to randomization question, Question A.6 (somewhat/very satisfied vs. other), Question A.26 (Could have refused to join START yes vs. no)*

- Multi-level logit models with random site effects (Stata's xtmelogit)
- Results of univariable models shown only if global Wald test was significant at the 0.20 level
- Model results shown as Odds Ratios and as %Risk differences
- In both cases, all comparisons are relative to the respective baseline category (usually the most prevalent).
- Continuous variables centered at the mean of their overall distribution thus risk differences
- in the case of continuous variables are relative to a typical person with the covariate of interest at the mean level.
- Risk differences and respective 95% CIs estimated through the Delta method (i.e. Stata's nlcom) and based on the estimate beta coefficients of the fixed effects and their variance-covariance matrix

Univariable/multivariable analysis– *Comprehension Score (0-16) and Satisfaction Score (0-8)*

- Quantile (median) regression with corrected SEs for clustering within sites (Stata's qreg2 - Parente, P.M.D.C. and Santos Silva, J.M.C. (2013), Quantile regression with clustered data, Department of Economics, University of Essex, Discussion Paper No 728.)
- Results of univariable models shown only if global Wald test was significant at the 0.20 level
- Model results shown as beta coefficients. All comparisons are relative to the respective baseline category (usually the most prevalent).

Univariable/multivariable analysis– *Voluntariness Score (0-4)*

- Ordinal logistic regression with corrected SEs for clustering within sites (Stata's ologit)
- Results of univariable models shown only if global Wald test was significant at the 0.20 level
- Model results shown as Odds Ratios (for higher scores)
- All comparisons are relative to the respective baseline category (usually the most prevalent).
- Due to violations of the proportionality of odds assumption, the dependent variable was recoded into a binary one (4 vs. <4) and logistic models were fitted (only for the multivariable models identified using the ordinal logistic regression)

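### The consent substudy hypothesises that the concise form is at least as well understood, but it sets no margin by which a near-null result could support that

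*Supplement*

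**What the plan says.** **Hypothesis.** The substudy analysis plan (26 Oct 2013) states that "comprehension for those receiving the concise consent form will be at least as good as for those who received the standard form". Protocol Version 2.0, Section 8.3.3, says the same. For satisfaction the plan predicts superiority: "Satisfaction will be higher in the concise group".

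**Use of the result.** Section 8.3.1 foresees that one form may prove superior, and then adds: "A demonstration of equivalent results would permit investigators to use the most efficient and easiest of equally effective alternatives".

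**Primary endpoint and sizing.** The endpoint is the "proportion of participants who answered the randomization questions correctly". Section 8.3.10 sizes the substudy by the number of sites that "are required to detect a difference of 15% of participants responding accurately to the questions concerning randomization" (50% versus 65%). The analysis plan repeats this target: "difference of 15% between participants receiving each consent who respond accurately to questions about randomization with a power of 0.80 at the two sided level" (alpha 0.05). Neither Section 8.3 nor the analysis plan gives a non-inferiority or equivalence margin, a one-sided test, or a rule that reads a confidence interval against a threshold.

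**Reporting of the arm comparison.** Section 8.3.11 says that the concise-versus-standard odds ratio and its 95% interval will be cited. The analysis plan likewise promises cluster-appropriate logistic regression with odds ratios and intervals for the primary outcome, and descriptive results by arm. For the binary outcomes it adds risk differences with 95% intervals.

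**Display rule.** In each of its three univariable/multivariable blocks the analysis plan says: "Results of univariable models shown only if global Wald test was significant at the 0.20 level". Consent arm is not mentioned as an exception.

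**The concern.** The comprehension hypothesis is non-inferiority in form, while the planned analysis is a test for a difference. Failing to find a difference is not evidence that there is no important deficit. Suppose the two forms are understood about equally well, which the hypothesis allows and Section 8.3.1 wants to act on. The plan then has no pre-specified way to say so. The substudy could end with a non-significant p-value presented as equivalence, or with a margin chosen after the result is known.

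The display rule is a separate and smaller matter. It is unqualified, so on a literal reading it could also govern the univariable consent-arm model, and it would bite most when the arms are similar.

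**Working it through.** **Inputs.** From Section 8.3.10: proportions 0.50 and 0.65, 25 participants per site, between-site coefficient of variation k = 0.30 for planning and k = 0.17 at re-assessment. From the analysis plan: 179 sites, 4,150 participants, intra-site correlation 0.09. From Section 8.3.6: 1:1 allocation of sites.

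**1. The plan's own figure.** The Hayes–Bennett formula gives sites per arm

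c = 1 + (1.96 + 0.8416)² × [p0(1−p0)/m + p1(1−p1)/m + k²(p0² + p1²)] / (p0−p1)²

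With k = 0.30 and m = 25 the bracket is 0.0100 + 0.0091 + 0.09 × (0.25 + 0.4225) = 0.0796. So c = 1 + 7.849 × 0.0796/0.0225 = 28.8, which rounds up to 29 per arm, or 58 sites and 1,450 participants. This matches the stated figure. It is a two-sided difference design, and no margin enters it.

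**2. Precision at the actual size.** Mean site size is 4,150/179 = 23.2, and sites per arm are 179/2 = 89.5. With both arms at 50% correct,

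SE = √{2 × [0.25/23.2 + k² × 0.25]/(89.5 − 1)}

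- k = 0.17: √(0.0360/88.5) = 0.0202; half-width 1.96 × SE = 4.0 points
- k = 0.30: √(0.0666/88.5) = 0.0274; half-width 5.4 points

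**3. Non-inferiority power if the forms are truly equal**, using Φ(margin/SE − 1.96), i.e. the lower limit of a two-sided 95% interval:

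| Margin (points) | k = 0.17 | k = 0.30 |
|---|---|---|
| 5 | 70% | 45% |
| 7.5 | 96% | 78% |
| 10 | 99.9% | 95% |

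The smallest margin with 90% power is 6.5 points (k = 0.17) or 8.9 points (k = 0.30).

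**4. What a non-significant result could mean.** Take the wider half-width of 5.4 points. An observed difference of 0 gives −5.4 to +5.4. An observed difference of −5 gives −10.4 to +0.4. Both are non-significant, and the plan does not distinguish them. Against a 7.5-point margin the first supports the hypothesis and the second does not.

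**5. The display rule, only if it were applied to consent arm.** A true null would be left out of the univariable table with probability 1 − 0.20 = 80%. At a true 3-point difference the probability is 42% (k = 0.17) or 57% (k = 0.30).

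**The case against.** The strongest reply concerns reporting. A reader might infer from the display rule that the arm effect disappears whenever the forms perform alike, that 80% suppression is to be expected, and that the reported arm effects are therefore biased away from zero. The documents do not support that. Section 8.3.11 and the analysis plan both commit to the primary-outcome arm odds ratio with its interval, with no p-value condition, and descriptive results are shown by arm. The rule covers univariable models only. Its surroundings (a global Wald test, a reference category that is usually the most prevalent, centred continuous variables) read most naturally as covariate screening. The percentages in step 5 are conditional on the less natural reading.

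A reader might also infer that the hypothesis can never be demonstrated. That too is stronger than the text allows. An interval wholly in favour of the concise form would show it without any margin, and a reader can hold a published interval against a margin of their own. Nor is an unadjusted contrast the only one that randomisation protects; an arm effect adjusted for baseline covariates is protected as well.

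Two things survive. No pre-specified reading exists for a near-null result. And the text is not explicit about the display rule. The unconditional promise of an interval covers the primary-outcome odds ratio, but not the risk difference or the comprehension, satisfaction and voluntariness scores. The by-arm descriptive tables do not fill that gap, because their chi-square, exact, rank and t-tests ignore clustering. At the plan's correlation of 0.09 the design effect is about 1 + 22.2 × 0.09 = 3.0.

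It is also fair to say that no document supports any particular margin.

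**Conclusion.** The point holds in this form: an at-least-as-good hypothesis is paired with a difference-only analysis, so a non-significant or near-null comparison cannot validly be read as supporting it. What is missing is the margin, not the precision, as steps 2 and 3 show.

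Those figures assume equal site sizes, full questionnaire completion and 50% correct in both arms. The primary analysis takes only participants who completed the questionnaire, and unequal sites or non-completion would widen the interval. The CV of 0.17 came from about 500 participants at 70 sites, roughly 7 per site, so 0.30 is a sensible pessimistic case. The calculation is for a difference in mean site proportions and only approximates the model-based risk difference that the plan describes.

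The display rule is a separate ambiguity and does not cause the missing margin. The satisfaction hypothesis is one of superiority and needs no margin. The main START comparison is not affected.

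**What to change.** 1. Before the arm comparison is seen, set and justify a margin on the risk difference for the primary endpoint. Half the planning difference, 7.5 points, is one example. Conclude that the concise form is at least as good only if the lower 95% limit for concise minus standard, from the cluster-adjusted model, lies above minus that margin. The analysis plan describes some modelling in the past tense (the recoding of the voluntariness score). If arm results have already been seen, label the margin post hoc.
2. State that the 0.20 display rule applies to covariates only, and that the cluster-adjusted arm estimate with its 95% interval is reported for every endpoint, including the secondary scores and the risk difference.

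The cost is about two sentences, since the risk difference and its interval are already planned for the binary outcomes. The downside is that a margin has to be defended.

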8.3.9 Study Outcome Measures

The primary endpoint will be the proportion of participants giving correct answers to questions about randomization. An important secondary endpoint will be based on mean scores on the comprehension section of the instrument. Comprehension will include questions on study purpose and procedures, randomization, risks and side effects, and right to refuse. A comprehension score will be based on the number of correct answers to the knowledge questions.

Other secondary endpoints will be measured by a composite score of the satisfaction questions, a composite score of the voluntariness questions, and an evaluation of IRB/IEC required changes to the consent documents.

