8.3.11 Data Analysis

The number and characteristics of sites assigned to use the standard and concise consent will be summarized. Baseline site characteristics will include primary language of participants and site staff and the background of the person administering the consent (e.g., physician, nurse, coordinator). Interested sites for which the Informed Consent substudy or sample informed consents were not approved by local ethics committees will also be summarized.

For sites participating in the Informed Consent substudy, demographic characteristics (e.g., age, gender, ethnicity) of participants consented will be compared. In addition, the number of participants at each site who refused to complete the post-consent questionnaire will be tabulated. Median (IQR) site size (number of participants consented with completed questionnaires) for each treatment group will be summarized.

Logistic regression appropriate for cluster randomized trials (hierarchical models) will be used to compare the standard and concise consent groups for the primary outcome. Odds ratios (concise versus standard consent) and 95% confidence intervals will be cited. Mean levels of continuous secondary outcomes will be compared using methods that account for the within-site correlation. The intra-site correlation coefficient will be cited for the primary and each secondary outcome.

The primary analysis will include all participants who completed the post-consent questionnaire. In a secondary analysis, participants who were consented and did not complete the questionnaire will be considered. In these analyses, participants will be counted as if they did not comprehend the consent questions.

Subgroup analyses will be conducted by primary language, the nature of differences between the standard and concise consent as judged by the Informed Consent Substudy team, age, gender, race/ethnicity, education, and previous participation in

research studies. Tests of heterogeneity will be performed to document differences among subgroups.

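### The consent-substudy analysis plan models the comprehension and satisfaction scores only by median regression, although the protocol and the plan's own overview call for a clustered comparison of means

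*Supplement*

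**What the plan says.** Protocol version 2.0, section 8.3.9, sets the comprehension endpoint: "An important secondary endpoint will be based on mean scores on the comprehension section of the instrument". The score is a count: "A comprehension score will be based on the number of correct answers to the knowledge questions". Section 8.3.11 adds: "Mean levels of continuous secondary outcomes will be compared using methods that account for the within-site correlation". It also promises an intra-site correlation coefficient for each secondary outcome.

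The Informed Consent substudy analysis plan (26 Oct 2013) repeats this in its overview: "Mean levels of continuous secondary outcomes accounting for within-site correlation, and using the intrasite correlation coefficient". Its modelling section for the two scores then specifies only "Quantile (median) regression with corrected SEs for clustering within sites", fitted with qreg2, with "Model results shown as beta coefficients". It mentions no jittering or smoothing for ties and gives no reason for using medians, although it does explain why the voluntariness score was recoded. The descriptive section allows t-tests or ANOVA in a few cases, with no allowance for clustering.

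**The concern.** Two problems meet here. The modelling section conflicts with the endpoint in the protocol and with the plan's own overview, so two analysts could follow the same plan and report different estimands.

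The median is also a poor summary for these scores. Comprehension takes at most 17 values. Satisfaction takes 9 if it is scored in whole points, as its range suggests. The unadjusted arm coefficient is a difference of two medians, so it stays at 0 while both medians fall on the same value and jumps by a point when one crosses to the next. The usual standard errors for quantile regression rely on a continuous density at the median, which a heavily tied score does not have.

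The substudy hypothesises that comprehension with the concise form is no worse and that satisfaction is higher. A coefficient of 0 forced by ties could be taken as support for the first and could hide a real gain in the second. Univariable results are shown only when the global Wald test reaches the 0.20 level, so such a zero might not be displayed at all.

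**Working it through.** **The plan's own figure.** No power is stated for the two scores. The stated 58 sites are for the binary primary endpoint, and they reproduce with the Hayes-Bennett formula:

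c = 1 + (1.96 + 0.84)² × [p0q0/m + p1q1/m + k²(p0² + p1²)] / (p0 − p1)²

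With p0 = 0.50, p1 = 0.65, m = 25 and k = 0.30, the bracket is 0.0100 + 0.0091 + 0.0605 = 0.0796, and c = 28.78. That is 29 sites per arm, 58 in all and 1,450 participants. The primary endpoint is unaffected by this point.

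**Inputs for the scores.** From the documents: 179 sites, 4,150 participants (about 23 per site), and an ICC of 0.09, which was estimated for the binary randomization item. Assumed: SD 2.5 on the 0-16 score, SD 1.5 on the 0-8 score, and the position of the median.

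**Ties.** 4,150/17 = 244 and 4,150/9 = 461 participants per score value on average.

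**Real difference, medians.** If a score is a rounded continuous quantity, its median is the integer nearest to the arm's centre. Two arms d points apart (d < 1) share that integer for a fraction 1 − d of possible positions. For d = 0.4 this is 60%; for d = 0.5 it is 50%. Simulation of 179 sites of 23 (within-site SD 2.5, site SD 0.5) agrees: a median difference of exactly 0 in about 60% and 50% of trials on average, ranging from about 0% to 100% with position.

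**Real difference, means.** Power = Φ(d/SE − 1.96), with SE² ≈ 2 × total variance × [1 + 22 × ICC] / (179 × 23/2).
- Site SD 0.5: ICC = 0.25/6.5 = 0.038, SE = 0.108, power 96% at 0.4 points and over 99% at 0.5.
- ICC 0.09: total variance 6.25/0.91 = 6.87, SE = 0.141, power 81% at 0.4 and 94% at 0.5.

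**Dependence on position.** Separate simulation, 0-16 score, SD 2.5, ICC 0.09, 300 runs per cell:

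| Position of lower arm | True shift 0.5: median difference exactly 0 | True shift 0.5: power for means | No shift: median difference of a full point | No shift: rejection for means |
|---|---|---|---|---|
| Mid-category (arms symmetric about it) | 98.7% | 96.3% | 0% | 3.7% |
| 11.25 | 1.7% | 95.0% | 1.0% | 5.7% |
| 11.4 | 16.0% | 95.7% | 29.0% | 6.3% |
| 11.5 (boundary) | 52.0% | 96.3% | 51.3% | 3.7% |

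Under no shift, the approximate clustered standard error called every full-point difference significant. On the 0-8 score at ICC 0.09, a 0.4-point shift gave 0 in 100% of trials mid-category, with 100% power for means. With no shift at a boundary, a full point appeared in 48%.

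**No difference, averaged over position.** Two medians differ when a boundary falls between the arms' estimated centres, so the average rate is the mean absolute difference of those centres, √(2/π) × SE. With site SD 0.5 this lies between 0.80 × 0.108 = 0.086 and, with the median's SE larger by √(π/2), 0.108: about 10%.

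**The case against.** The overview still promises clustered means and the intra-site correlation, so the modelling section can be read as adding covariate models to that comparison. This stands: a reader might infer that the mean comparison was dropped, but the text shows only that the two parts are unreconciled. It does not rescue the plan, because median regression is the only clustered model named for these scores.

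The section also covers multivariable models. With a strong continuous covariate the adjusted median coefficient became fractional and close to the mean difference; with a weak one it usually stayed at 0 or a full point. The problem is therefore fullest in the unadjusted randomized comparison.

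Satisfaction is also analysed through Question A.6 in a multilevel logit with random site effects, so the satisfaction hypothesis does not rest on the median alone. The descriptive by-arm tests respond to shifts within ties, but with no stated allowance for site.

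Section 8.3.9 sets means for comprehension only. Satisfaction is a composite score, and it comes under the mean comparison only if it counts as a continuous outcome in section 8.3.11.

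**Conclusion.** The conflict is textual and needs no assumption: the modelling section departs from sections 8.3.9 and 8.3.11 and from the plan's own overview. Following the modelling section as written can report no difference when mean comprehension clearly differs, or a full point when nothing differs.

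The size depends on an unknown score distribution. A reader might infer that the method would nearly always miss a half-point shift, or would raise a false one-point difference half the time. The documents support neither as a general rate. The first needs both arms inside one category and the second needs the median on a boundary, so one score cannot show both at those rates. Averaged over positions, the figures are about 50-60% zeros for a true shift of 0.4 to 0.5 points and about 10% spurious points. The power for means rests on the assumed SD and on an ICC borrowed from a binary item. The standard errors in the simulation approximated those of qreg2, but the 0 and one-point estimates do not depend on them.

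This concerns secondary endpoints of a substudy and should be corrected.

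**What to change.** Reconcile the modelling section with the overview and with sections 8.3.9 and 8.3.11 by making a clustered comparison of means the main analysis of both scores. A linear mixed model with a random site effect, adjusted for the language stratum used in randomization, would do. This is a proposal: section 8.3.11 asks for allowance for within-site correlation but names no model for these scores. Report the mean difference between arms, its 95% confidence interval and the ICC, whether or not the 0.20 display rule is met. Keep medians or median regression as descriptive or supportive. If the sponsor prefers medians as the main analysis, the plan should give the reason and say how ties are handled.

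The cost is a change of wording in the analysis plan and re-running the models for two scores; no new data are needed.
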